5.1. STATISTICAL ANALYSIS PLAN

It should include a plan for analysis of primary and secondary outcomes, subgroup analyses if planned, and for handling of missing data and subjects who die or are lost to follow-up.

Primary Outcome:

Hypoxemic episode (SpO2 <85% for >10s) frequency

Secondary Outcome(s)

Frequency of Hypoxemia (SpO₂<85%), Bradycardia (HR<100/min), Bradycardia episode (HR<100/min for \geq 10s); Apnea (RR=0 for >20s, or RR=0 for \geq 10s + SpO2 <85% or HR<100/min); BPD defined using physiologic definition at 36w PMA

Aim 1: Statistical calculations will be performed using SPSS. Parametric tests will be used for analyses of all continuous variables except for comparisons involving the incidences of specified ranges of IBIs, which is a skew distribution. Nonparametric tests will also be used for analyses of ordinal datasets. The Kolmogorov-Smirnov (one-sample) and Friedman's and Wilcoxon signed-rank tests will be used for the nonparametric analyses. For factorial analyses of parametric data, separate repeated-measures ANOVAs will be used. For factors with more than two levels, the Greenhouse-Geisser correction will be used, and ε with unadjusted degrees of freedom will be reported. Where a main effect was observed for factors with more than two levels, post hoc tests using the Bonferroni adjustment will be done. Values will be expressed as means and SD, and *p* values (2-tailed) of <0.05 considered statistically significant. Pearson product-moment correlation coefficient analysis will be used to establish the association between pathological pauses in breathing and breathing stability.

Aims 2 and 3: As in Aim 1, we will quantify IBI and IBI variability as defined earlier (2, 4). Also as in Aim 1, other outcomes will include (i) hypoxemic time –the % time with $SpO_2 <90\%$, (ii) moderate hypoxemic time with $SpO_2 <80\%$ and severe hypoxemic time with $SpO_2 <60\%$ (iii) bradycardic time – % time with HR <100, (iv) severe bradycardic time – % time with HR <60, (iv) hypoxemic, bradycardic, or apneic episodes – the number of episodes of $SpO_2 <90\%$, $SpO_2 <80\%$, $SpO_2 <60\%$, HR<100, HR<60, or RR=0, respectively, for >10 seconds, with the episode length defined as the number of seconds of data values below the threshold, (v) cerebral hypoxemic episodes (decrease in $r_cSO_2 <50\%$ or of 20% from baseline for >1 minute) and somatic hypoxemic episodes (decrease of 20% from baseline in peri-renal area).

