4.3. POTENTIAL RISKS AND BENEFITS TO SUBJECTS

Potential Risks:

This study is primarily an observational study (Aim 1), and comparative effectiveness research (Aims 2 and 3), and is hence of low risk. Infants enrolled in this study are intrinsically at high risk, as they are born extremely preterm with a risk of death exceeding 20% and death or disability exceeding 50%, but participation in this study adds only minimally to the underlying risk.

For Aim 1, we will collect physiologic data from patient monitors, and clinical data on patient characteristics, illness severity, and outcomes from the medical records of the 120 enrolled infants. The primary risks are those of loss of confidentiality and privacy. Results and their linked clinical data will then be assigned an unique identifying code and anonymized to minimize risks to confidentiality. Only the PI and research coordinator will have access to patient data before anonymization. No patient identifiers will therefore remain in the data set that will be transmitted to the Data Coordinating Center.

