5.2. SAMPLE SIZE AND POWER ESTIMATES

Aim 1: A sample size of 100 infants per group is sufficient to detect a 20% change in a parameter related to an outcome using standard parametric or nonparametric tests (e.g. Wilcoxon signed-rank) at 80% power, α =0.05, with expected standard deviation of change of 50%. We plan to enroll 120 to account for attrition due to early death. Statistical power of 80% for detecting 20% difference in parameters is maintained even if the incidence of outcome (e.g. BPD) is only 20% of enrolled (24 of 120) infants if the standard deviation is 40% or less (as is expected to be, based on preliminary studies).

Aim 2: A sample size of 16 infants is sufficient to detect a 30% change in a parameter related to an outcome using standard parametric (e.g. paired t-test) or nonparametric tests at 80% power, α =0.05, with expected standard deviation of change of 40%. Hence, enrollment of 25 patients will be sufficient, even if there is attrition of up to 5 patients due to death, and data from 4 patients has technical issues with usability.

Aim 3: As in Aim 2, 16 infants are sufficient to detect a 30% change in a parameter related to an outcome by standard parametric (e.g. paired t-test) or nonparametric tests at 80% power, α =0.05, with expected standard deviation of 40%. Hence, enrollment of 25 patients will enable detection of even minimal changes, or of changes in parameters with much variation.

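### Aim 1's repeated-measures ANOVA and Friedman tests keep only infants observed at every level, and the plan names neither the repeated factor nor a rule for missing windows or deaths

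*Combined protocol and SAP*

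**What the plan says.** Section 5.1 assigns parametric and nonparametric tests to Aim 1, to be run in SPSS. On the parametric side: "For factorial analyses of parametric data, separate repeated-measures ANOVAs will be used", with a Greenhouse-Geisser correction and Bonferroni post hoc tests for factors having three or more levels. On the other side, "Friedman's and Wilcoxon signed-rank tests will be used for the nonparametric analyses", together with a one-sample Kolmogorov-Smirnov test. The within-infant factor is not named.

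The section opens with an instruction that the plan should include "handling of missing data and subjects who die or are lost to follow-up". No such rule follows for any aim.

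Section 4.2.4 schedules 96 hours of intensive recording for each Aim 1 infant at 2 weeks postnatal age, 32 weeks PMA and 36 weeks PMA. It adds sleep studies at 36 weeks and 3 months, and short samples of HR, RR and SpO2 on two days of each hospital week.

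On losses, section 5.2 says for Aim 1: "We plan to enroll 120 to account for attrition due to early death". For Aim 2 it tolerates up to 5 deaths among 25 infants and the case where "data from 4 patients has technical issues with usability". Section 4.3 describes the infants as "born extremely preterm with a risk of death exceeding 20" percent.

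**The concern.** Standard repeated-measures ANOVA and the Friedman test need a value at every level of the factor. An infant lacking one level is dropped entirely, including the levels it did supply. A plan that names these tests and is silent on missing data has therefore adopted listwise deletion without choosing it.

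The three windows are the most natural repeated factor. Aim 1 has no interventions; the sleep studies give only two levels; and the twice-weekly samples give each infant a different number of levels. On that reading, an infant who dies at 33 weeks PMA loses its 2-week and 32-week recordings from these tests, and so does a survivor with one failed recording.

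Two things are at stake. Recordings that are costly to obtain go unused. And the result describes survivors with three good recordings, in an aim about resilience and risk, without the plan saying that this is the intended population.

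**Working it through.** **The plan's own figure.** Section 5.2 states: "A sample size of 100 infants per group is sufficient to detect a 20% change in a parameter related to an outcome", at 80% power and alpha 0.05 (two-tailed in 5.1), "with expected standard deviation of change of 50" percent. The standardised effect is 20/50 = 0.4.
- Two-group comparison of means: 99 per group, or 99.1 by the t distribution, so the stated 100 is reproduced.
- Paired comparison: 50 (normal), 52 (t) or 54 (Wilcoxon).
- The 100 is thus a two-group number, although the text names a paired test. That is a separate matter.
- Enrolment: 100 / (1 − 20/120) = 120. The Aim 1 allowance is therefore 20/120 = 16.7%, for early death only.

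**Inputs for the check.**
- Enrolled: 120 (section 5.2).
- Death, d: 16.7% (implied by 5.2) or 20% (the floor of the population risk in 4.3).
- Technical loss per window, t: 4/25 = 16%. This is an Aim 2 tolerance for a single window; using it for Aim 1 is an assumption.
- Windows: three (section 4.2.4), assumed to be the repeated factor.

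**Complete infants, death only:** 120 × (1 − d) = 100 at 16.7% and 96 at 20%.

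**Complete infants with technical loss (illustration), d = 20%, t = 16%:**
- Same infants fail every time: 120 × 0.80 × 0.84 = 80.6, or 81.
- Failures independent across windows: 120 × 0.80 × 0.84³ = 56.9, or 57.
- With d = 16.7%: 59 to 84. With d = 20% and t = 4/20 = 20%: 49 to 77.

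**Recorded windows discarded (d = 20%, t = 16%).** Assume deaths fall after the 2-week window, half before and half after the 32-week one. Recorded windows are 0.84 × (120 + 108 + 96) = 272.
- Overlapping failures: 3 × 80.6 = 242 kept, 30/272 = 11% lost.
- Independent failures: 3 × 56.9 = 171 kept, 101/272 = 37% lost.
- If instead every death precedes the 2-week window, 0.84 × 3 × 96 = 242 windows are recorded, and the loss is 0% (overlapping) or 1 − 171/242 = 29% (independent).

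**Power of a paired test (effect 0.4, two-sided 0.05):** 84% at n = 57, 94–95% at n = 81, 97% at n = 96 and 78% at n = 49.

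**Simulation** (250 runs; total SD 50% and within-infant correlation 0.5, so SD of change = √(2 × 0.25 × 0.5) = 50%; true change −20%; about 20% deaths after the 2-week window; 16% technical loss per window):
- Death unrelated to the measurement: complete cases are unbiased with 85% power, against 96% for a mixed model on all windows. An independent re-run gave 83% and 95%.
- Odds of death assumed to double per SD of the 2-week value: complete cases −16.6%, mixed model −20.2%. In that setup the true change among survivors is about −16.8%. The −20% averages in about −33% for infants who died: 0.80 × (−16.8) + 0.20 × (−33) = −20.0.

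**The case against.** The strongest reply is that the factor is inferred. Section 5.1 does not say that the windows are its levels and states no complete-case rule. The Aim 1 hypotheses in 3.1 and 3.2 concern predicting episodes in individual infants and patterns associated with BPD, not change across windows. This stands, and it is why the point is conditional. It does not answer the missing rule, which 5.1's own opening asks for.

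Several stronger readings are tempting and are not supported:
- A reader might infer that the plan's own rates predict 57 to 81 analysable infants. The 16% is an upper tolerance from Aim 2, and the 20% is a background risk. The only Aim 1 allowance leaves 100.
- A reader might infer that every infant who dies is lost. Only deaths before a completed 36-week window matter, and only in tests that need all levels. Wilcoxon pairs, single-window analyses and the twice-weekly samples can retain these infants. Conversely, an infant who dies before 2 weeks contributes no window to any model.
- A reader might infer a proven bias of −16.6% against −20%. The link between death and the measurement is assumed, and the complete-case figure is about right for survivors. The mixed model reaches −20% by extrapolating past death.
- A reader might infer that power collapses. At 57 to 81 it does not.
- A reader might infer that the ANOVA assumes equal spacing of the windows. A categorical time factor does not.

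**Conclusion.** The point holds as a gap in specification with a practical cost. The named all-level tests delete incomplete infants by default, and nothing in the plan says whether that is intended. If the three windows are the factor, between 96 and 100 of 120 infants remain on death alone, and 57 to 81 under the borrowed technical-loss figure.

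The firm cost is precision. Under the illustrative inputs, 11% to 37% of recorded windows go unused if deaths fall after 2 weeks. Power is about 85% rather than 96% where failures are independent. The gain is smaller where the same infants fail repeatedly, because paired power at n = 81 is already 94–95%. The second cost is a result limited, without saying so, to survivors with complete recordings. Whether that is a bias depends on how death relates to instability and on which estimand is wanted, and the documents settle neither. This should be corrected before analysis, but it does not by itself undermine Aim 1.

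**What to change.** Amend the Aim 1 part of section 5.1 as follows.
- Name the repeated factor and its levels for each analysis.
- Replace the repeated-measures ANOVAs with a linear mixed model in SPSS using every recorded window, with a random infant effect and PMA at recording as a covariate. PMA matters because the gap from 2 weeks of age to 32w0d is 224 − 154 − 14 = 56 days for birth at 22w0d and 224 − 202 − 14 = 8 days at 28w6d.
- For the skewed IBI-range counts, use a generalized mixed model instead of Friedman.
- State whether the target is the change while alive or the change among survivors to 36 weeks. Report the survivor-only result as a sensitivity analysis, because the mixed model otherwise extrapolates past death. Survivors with a missing window can stay in that analysis.
- State how unusable windows are defined, and report how many infants and windows enter each analysis.

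The cost is SAP wording and slightly more analysis work, with the same software and no new data. The downside is reliance on a missing-at-random assumption. The choice should be fixed before anyone examines which infants have missing windows.

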		5.5.2. Data Monitoring Plan and Stopping Rules. Error! Bookmark no			
Section 6.	Refer	ences	20		
	-		-		

SECTION 1. ABSTRACT

Study Objective

Prospectively define and validate ventilatory mechanisms associated with resilience against or risk for development of impaired oxygenation at 36 weeks' postmenstrual age (physiologic definition of BPD) and at follow-up (corrected age of 3 months)

Study Design Type

Aim 1: Prospective Observational Study

Aims 2 and 3: Randomized Cross-over Comparative Effectiveness Trial

Eligibility Criteria

Aim 1: This study will enroll neonates in our Regional NICU (RNICU) at UAB as follows: **Inclusion**:

- Inborn infants weighing 401-1,000 grams on admission and/or 22^{0/7} to 28^{6/7} (<29 weeks) inclusive completed weeks of gestation,
- Infants eligible for full care and resuscitation as necessary, and surviving beyond 24 h of age
- Enrollment at <1 week post-natal age
- Informed consent from parent/guardian

Exclusion

- Refusal or withdrawal of consent
- Major congenital malformations (e.g., not including patent ductus arteriosus, small hernia)

Aim 2: This study will enroll the subset of infants from Aim 1 who are still intubated or on nasal IMV at 2 weeks postnatal age, meet blood gas criteria (arterial or capillary arterialized blood gas values done q12-24h, as most infants do not have an arterial line at 2 weeks: pH >7.25, PaCO₂ >40 mm Hg), have TcCO₂ monitoring with TcCO₂ values that trend and correlate appropriately with PaCO₂, and are not judged too unstable by the Attending neonatologist.

Aim 3: This study will enroll the subset of infants from Aim 1 who are receiving oxygen supplementation at 32w and 36w PMA, and are not judged too unstable by the Attending neonatologist.

Study Intervention/Methods

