After parental consent is obtained, infants will be enrolled in prospective collection of continuous physiologic data from vital signs monitors (HR, RR, SpO₂). In addition, intensive multiparametric physiologic monitoring and data collection (96 hours each) at three distinct time frames: 2 weeks postnatal age, 32 weeks post-menstrual age (PMA), 36 weeks PMA will be done, along with a sleep study at 36 w PMA and 3 months corrected age. Aim 1 will be observational, using physiological data to develop predictive mathematical models for outcomes. Aim 2 will determine if late (at or beyond postnatal day 14) mild permissive hypercapnia is associated with reduction in apnea, bradycardia, and hypoxemic episodes and with improved stability of oxygenation. Aim 3 will determine if servo-controlled oxygen environment is associated with reduction in hypoxemic episodes and improved stability of oxygenation, as compared to oxygen administered by nasal cannula.

Primary Outcome

Hypoxemic episode (SpO2 <85% for 10s) frequency

Secondary Outcome(s)

Frequency of Hypoxemia (SpO₂<85%), Bradycardia (HR<100/min), Bradycardia episode (HR<100/min for \geq 10s); Apnea (RR=0 for >20s, or RR=0 for \geq 10s + SpO2 <85% or HR<100/min); BPD defined using physiologic definition at 36w PMA

SECTION 2. CONFLICT OF INTEREST DISCLOSURES

Per Title 42, Code of Federal Regulations, Part 50, Subpart F (50.604 Responsibilities of Institutions regarding Investigator financial conflicts of interest), as amended, institutions and all subrecipients are required to notify the grants officer of any financial conflicts of interest (FCOI) prior to expenditure of any funds and within 60 days of any subsequently identified FCOI.

Financial Conflicts of Interest of the Institutions and Investigators No conflicts of interest exist with commercial entities.

SECTION 3. STATEMENT OF PROBLEM

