3.1. PRIMARY HYPOTHESIS OR QUESTION

Aim 1: We hypothesize that mathematical models of personalized ventilatory patterns based on multiparametric vital signs monitoring and signal analysis methods will be able to predict hypoxemic episodes in individual infants before they occur.

Aim 2: We hypothesize that late (at or beyond postnatal day 14) mild permissive hypercapnia is associated with reduction in hypoxemic episodes

Aim 3: We hypothesize that servo-controlled oxygen environment is associated with reduction in hypoxemic episodes, as compared to oxygen administered by nasal cannula

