4.2.4. Study Intervention and Comparison

Aim 1:

This is a non-interventional observational study, in which we will use the data from the intensive multiparametric physiologic monitoring of 96 hour duration at each of the three time points of 2 weeks postnatal age, 32 weeks PMA, and 36 weeks PMA as well as the polysomnography at 36w PMA and 3 months follow-up for this Aim. In addition, we will use a random sampling (3 continuous h/day of 2 days (Mon/Thurs) in each week of the infant's hospital stay) of the continuous data recording of HR, RR, and SpO₂ from enrollment to discharge. These data will be combined with clinical data during the hospital course as well as during follow-up, specifically data on respiratory or feeding support.

Data used will include HR, RR, SpO₂, ventilator/O₂ supplementation, $P_{ET}CO_2$ (end tidal CO₂ by microcapnography), T_CCO_2 (transcutaneous CO₂), r_cSO_2 (near-infrared cerebral oximetry), r_sSO_2 (near-infrared somatic oximetry), and temperature. Data acquisition, band-pass filtering, and wavelet transforms of the signals will be done as described (2, 4, 6, 29).

We will develop mathematical models of ventilatory patterns to predict apneic, hypoxemic and/or bradycardic episodes in individual infants before they occur. We will quantify the irregularity in breathing using the IBI and IBI variability as defined earlier (2, 4). The normal IBI is around 1 second, but due to the irregular breathing pattern in preterm infants, this may vary from <1s to 20s or longer. For this study, we will define eupnea as IBI <2s and apneic range as IBI>5s as done previously (29). The basic assumptions of the point process model for breathing are that peak inspiration (maximal inspiratory effort as recorded non-invasively) is a discrete event marked by neuronal inspiratory burst and that IBI dynamics are governed by multiple feedback and feed-forward loops modulating the respiratory oscillator. In addition to the respiratory signal, we will develop models using the ECG and SpO₂ signals plus respiratory signals to determine if accuracy is improved. We have developed point process models for the evaluation of bradycardia and its severity.

Aim 2:

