(a) We will use the data from the 96 hours of intensive multiparametric physiologic monitoring at 2 weeks postnatal age. The first 24h of the data collection will be the baseline data. Over the next 72h, we will evaluate 3 interventions in a cross-over manner, with the initial intervention randomly assigned (computer-generated): Intervention 1 (24-48h of data), Intervention 2 (48-72h), and Intervention 3 (72-96h). For example, Intervention 1 may be to increase TcCO₂ by 5 mm Hg above baseline (at the time of capillary blood gas) and maintain at that level (by reducing IMV rate or pressures, by clinician decision) for 24h, and Intervention 2 will be to decrease TcCO₂ by 5 mm Hg back to initial values (by increasing IMV rate or pressures, by clinician decision) for 24h, and Intervention 1 (to increase TcCO₂ by 5 mm Hg) to validate that results of Intervention 1 are due to increased PCO₂ and less likely to be random fluctuations. On the other hand, if Intervention 1 is to decrease

 $TcCO_2$ by 5 mm Hg (from baseline at time of capillary blood gas) and maintain at that level (by increasing IMV rate or pressures) for 24h, and Intervention 2 will be to increase $TcCO_2$ by 5 mm Hg back to initial values (by decreasing IMV rate or pressures) for the next 24h. Intervention 3 will be to repeat Intervention 1. These interventions are chosen so that we will be able to evaluate the effects of altering $PaCO_2$ on respiratory irregularity while maintaining the pH at or above 7.2, generally regarded as a safe threshold. At the conclusion of interventions and data collection, infants will be managed according to the Clinician's preference.

Aim 3:

For infants on oxygen supplementation at 32w PMA, we will use the data from the 96 hours of intensive multiparametric physiologic monitoring at 32w PMA. For infants on oxygen supplementation at 36w PMA, we will use the 96 hours of intensive multiparametric physiologic monitoring at 36w PMA as well as data from the sleep study

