(b) The first 24h of the data collection will be the baseline data. Over the next 72h, we will evaluate 3 interventions in a cross-over manner: Intervention 1 (24-48h of data), Intervention 2 (48-72h), and Intervention 3 (72-96h). Initial intervention will be by random assignment (computer-generated). For example, Intervention 1 may be to switch the infant to the servocontrolled O_2 environment at a range necessary to maintain the optimal SpO₂ (91-95%). As this may not be the same FiO₂ as that by cannula, we will calculate the effective hypopharyngeal FiO₂ using formulae incorporating FiO₂, cannula flow, and minute ventilation (24-27) and adjust from this FiO₂. The first 12h will be for identifying the appropriate FiO₂ and stabilizing tracings, and the second 12 h will be data collected for analysis. Intervention 2 will be then be switching the infant back to the cannula at the FiO₂ and flow rate the infant was receiving in the first 24h (unless the FiO₂ or clinical status had markedly changed in the previous 24h and adjustments are necessary), with analysis of data in the second 12h after stabilization. Intervention 3 will be switching back to the servo-controlled O_2 environment for 24h. Similarly, for infants for whom Intervention 1 is switching to a cannula, Intervention 2 will be back to the O_2 environment, and Intervention 3 back to the cannula. At the conclusion of interventions and data collection, infants will be managed according to the Clinician's preference.

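### Aim 1's primary hypothesis is that hypoxemic episodes can be predicted before they occur, but the Aim 1 analyses in 5.1 assess only fit, difference or association and so do not test it

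*Combined protocol and SAP*

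**What the plan says.** Prediction is the stated purpose of Aim 1. Section 3.1 says that the models "will be able to predict hypoxemic episodes in individual infants before they occur", and 3.2 extends this to bradycardia, hypoxemic and bradycardic time, and apnea. The abstract (Section 1) describes Aim 1 as "using physiological data to develop predictive mathematical models for outcomes" and opens its objective with "Prospectively define and validate ventilatory mechanisms associated with resilience against or risk for development of impaired oxygenation". In 4.2.4 the investigators add: "we will develop models using the ECG and SpO₂ signals plus respiratory signals to determine if accuracy is improved".

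The Aim 1 analyses in 5.1 are parametric tests for continuous variables, one-sample Kolmogorov-Smirnov, Friedman, Wilcoxon signed-rank, repeated-measures ANOVA with Greenhouse-Geisser and Bonferroni adjustments, and a correlation: "Pearson product-moment correlation coefficient analysis will be used to establish the association between pathological pauses in breathing and breathing stability". Section 5.2 sizes Aim 1 for a 20% change in a parameter: 100 infants per group, SD 50%, 80% power, alpha 0.05.

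The Aim 1 data (4.2.4) are three 96-hour intensive recordings, the sleep studies, and a sample of the continuous HR, RR and SpO2 record: "we will use a random sampling (3 continuous h/day of 2 days (Mon/Thurs) in each week".

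**The concern.** A claim of prediction needs three things fixed: how far ahead the model must warn, how its success is scored, and on which data. The plan gives none of them. The word accuracy in 4.2.4 has no definition, and validation in the abstract and in 4.3 has no procedure.

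A listed test could therefore return p<0.05, for example because a breathing index differs on average before episodes, and be reported as support for the primary hypothesis while predictive performance is weak or was never measured. The comparison of signal sets has a related gap. The plan does not say which data accuracy is computed on, and fitting data would favour the model with more signals.

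**Working it through.** **1. Hypothesis against analysis (3.1, 4.2.4, 5.1).**
- Kolmogorov-Smirnov: does a model's distribution fit? It does not ask whether an episode is foreseen.
- Friedman, Wilcoxon signed-rank, repeated-measures ANOVA: does a quantity differ between conditions or times within infants?
- Pearson: breathing pauses against breathing stability. This is the only pair of variables named. Hypoxemic episodes are not in it, and it has no time order.
- Nowhere in the document: sensitivity, specificity, AUC, false-alarm rate, calibration, lead time, held-out or cross-validated data, or a success criterion. The background in 3.3 reports goodness of fit and changes around apnea, not predictive performance.

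**2. What 5.2 sizes.** The standardised effect is 20/50 = 0.4. For two groups, n = 2(1.960 + 0.842)²/0.4² = 98.1, so 99 per group; the t-test version gives 99.1, so 100, with 80.4% power at 100. The plan's figure reproduces as a two-sample difference in means. Read as a paired change, 52 infants would suffice and 100 would give 97.7% power. On either reading it sizes a difference, not predictive performance.

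**3. Illustration: can a weak predictor be significant?** The plan does not specify this comparison; it is one use of the listed repeated-measures tests.
- Assumed: each infant gives e pre-episode windows and 4e control windows; within-infant SD is 1; infant effects are normal with mean d and SD τ; N = 100 (from 5.2); two-sided 0.05.
- e = 200 is 50 episodes a day (a cited study in 3.3, not shown to use the <85% threshold) × 4 days; e = 20 allows for clustering. τ runs from 0.1 to 0.5.
- AUC = Φ(d/√2), so AUC 0.55 gives d = 0.178. Averaged over infants at τ = 0.5, it is Φ(0.178/√(2 + 0.25)) = 0.547, still about 0.55.
- Variance of an infant's mean difference: V = τ² + 1/e + 1/(4e). With two levels, repeated-measures ANOVA is the paired t-test, with noncentrality d√N/√V on 99 df.

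| e | τ | V | noncentrality | power |
|---|---|---|---|---|
| 20 | 0.5 | 0.25 + 0.05 + 0.0125 = 0.3125 | 1.78/0.559 = 3.18 | 0.88 |
| 200 | 0.5 | 0.25 + 0.005 + 0.00125 = 0.25625 | 1.78/0.506 = 3.51 | 0.94 |
| 20 | 0.1 | 0.01 + 0.05 + 0.0125 = 0.0725 | 1.78/0.269 = 6.6 | 1.00 |

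For an AUC of 0.53 (d = 0.106) the same calculation gives 47% (e = 20, τ = 0.5) to 100%.

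**The case against.** **The listed tests could serve.** Paired tests such as Wilcoxon signed-rank can compare two models once each infant has an accuracy score. That is right, and it is a reason to keep them. But 5.1 defines no such score.

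**The illustration tests something the plan does not state.** This is also right: the window comparison, the 4:1 controls and the episode counts are assumptions. The illustration shows only that significance and useful prediction can come apart. The defect rests on the text.

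**Weak single features do not imply weak models.** This stands. The hypothesis concerns personalized patterns, and a model that uses each infant's own effects can do much better than one feature's average when infants differ. A reader might infer that Aim 1's models will predict poorly. The documents give no basis for that, nor for any expected accuracy.

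**BPD and the other infant-level outcomes.** A reader might extend the criticism to these. The secondary hypothesis in 3.2 is worded as identifying patterns associated with them, which difference and association tests suit, so the point stays with episode-level prediction.

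**Cited methods papers may supply the detail.** Section 4.2.4 cites them for signal processing and for defining interbreath intervals, not for scoring predictions.

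**Conclusion.** The concern holds for Aim 1's primary hypothesis. Carried out as written, 5.1 would not test whether hypoxemic episodes are predicted in individual infants before they occur. This is more than missing detail, because the analyses that are named answer other questions. It should be corrected before Aim 1 data are analysed; the data themselves remain usable.

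Under the stated assumptions, a feature averaging an AUC of 0.55 within infants reaches significance with 88% to 100% power. The conclusion does not depend on that range.

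A reader might also infer that accuracy will be computed on the fitting data and will therefore be inflated. The plan does not say so; it leaves the evaluation data open.

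**What to change.** In 5.1, make the primary Aim 1 analysis episode-level predictive performance on data not used for fitting. Fix in advance a lead time and one performance measure, for example AUROC, or sensitivity at a stated false-alarm rate. Give confidence intervals that resample infants.

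- **Personalized models:** use a time-ordered split of the same infant's recordings that does not coincide with a change of intervention. In Aim 2, "Over the next 72h, we will evaluate 3 interventions in a cross-over manner, with the initial intervention randomly assigned", and Aim 3 has the same three-period structure. In both, "The first 24h of the data collection will be the baseline data". A split at 24, 48 or 72 hours in these infants would mix prediction error with the effect of the change. Splitting inside the baseline day or inside one condition avoids this.
- **Population models:** use cross-validation that keeps each infant's data in one fold.
- **Signal sets:** compare respiratory-only with respiratory, ECG and SpO2 models on the same held-out predictions from the 96-hour recordings. The weekly samples are described only as HR, RR and SpO2, so use them for this only if they hold the waveforms needed.
- **Listed tests:** keep them as supporting analyses; the paired ones may be applied to per-infant scores.

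The cost is SAP wording, more analysis work, a probably lower reported accuracy, and some loss of usable hours in Aim 2 and 3 infants. The size of that loss cannot be computed. Section 5.2 calls 25 infants sufficient for Aim 2 and plans 25 for Aim 3 but caps neither, and infants still on respiratory support or oxygen may contribute a large share of the episodes.
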